Side effects of DCS in human beings have been minimal. DCS has been widely used in the treatment of tuberculosis (500mg per day or higher), without causing neurotoxicity (e.g., Rivas Salazar, 1970). Goff et al. (1999) reported that only one patient dropped out of a schizophrenia study because of vague somatic discomfort. van Berckel et al. (1997) tested DCS in healthy participants and found that it was well tolerated and did not induce any side effects. In our recent trial examining the efficacy of DCS augmentation of behavior therapy for Obsessive Compulsive Disorder, no subjects reported any side effects as a result of the medication. DCS readily crosses the blood-brain barrier (Hanngren, Hansson, & Ullberg, 1961). Its half-life in serum is approximately 7 to 15 hours (Nair, Epstein, Baron, & Mulinos, 1956).

Altogether, when added to exposure therapy, DCS seems to be a promising treatment for patients suffering from anxiety. In the current study, we are planning to investigate DCS augmentation of exposure therapy for BDD. Consistent with our previous trial of DCS in OCD, we intend to administer 100mg of DCS one hour before each treatment session. The dose was chosen on the basis of a literature review and personal communication with [name] and [name] (the lead-author of the above mentioned DCS height phobia trial). The timing of the dose relative to the therapy session was chosen on the basis of feedback from [name]. As noted above, Ressler et al. (2004) found a significant reduction of height phobia severity

with 500mg/d of DCS, and they did not report any side effects at this dosage. In order to test whether DCS specifically works through augmenting fear extinction within ERP, DCS will only be administered one hour before each treatment session, and not on a daily basis. This will be in contrast to Goff et al. (1995), who administered DCS daily to improve negative symptoms in schizophrenia, but in accord with Ressler et al., (2004) who only gave DCS prior to each behavior treatment session for height phobia.

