At the initial visit, we will first obtain informed consent from the participant. We will also have participants sign their initials and date if they consent to sharing their de-identified data with other researchers in our group or across studies for research purposes only. This procedure will save subjects time if they participate in more than one study at our clinic because it will eliminate repeating assessments shared between studies. The participant will then undergo a structured clinical interview and fill out several questionnaires assessing BDD symptoms, anxiety, and depression. If the participant is eligible for participation based on this evaluation, the study physician will then meet with him or her to conduct the medical evaluation (more detail below). If the participant remains eligible for the study after the medical evaluation then he or she will be randomized to receive either the D-cycloserine or placebo. The MGH research pharmacy will create and maintain the coded randomization schedule for this double-blind design and prepare and dispense the study medication (DCS or placebo) to study staff. None of the investigators will be privy to the code, except for the study physician in case of an emergency. Participants who choose to participate in the optional genetics component of the study will also have their blood drawn at this visit. In all, the initial visit will last approximately 3-4 hours. After randomization, the participant will come to the clinic for a psychoeducation/treatment planning session approximately one week later (see below for more detail). If we are unable to schedule the treatment planning session within 21 days of the screening visit, participants will be asked to complete a modified screening session directly prior to the treatment planning session. This visit will take approximately 30 minutes. This visit will last approximately 1.5 to 2 hours. The participant will not take the study medication/placebo prior to this visit. After this treatment planning session the participant will be scheduled for 10 once weekly behavior therapy sessions over a 10 week period. The first two therapy sessions will involve primarily cognitive interventions and so the study medication will not be administered prior to these sessions. The participant will be asked to come to the clinic one hour before sessions 3-10 to take the study medication/placebo in the presence of the therapist. Study medication will be kept at the clinic for the duration of the study. In addition to the therapy visits, comprehensive assessments of BDD symptoms, mood state and cognitions to assess the outcome of therapy will be given at midtreatment (after session #5), post treatment and at 1- and 6- month follow-ups. These assessments will take approximately 1 hour. BDD symptoms, CGI-I score, and depressive symptoms will be assessed via self-report questionnaires at every treatment session. These questionnaires

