
will take approximately 5 minutes to complete. A detailed assessment schedule is submitted for review.

Psychological Assessments

Comprehensive assessments of BDD symptoms, mood state and cognitions to assess the outcome of therapy will be given at pretreatment, midtreatment, post treatment and at 1- and 6- month follow-up. BDD symptoms, CGI-I score, and depressive symptoms will be assessed every treatment session.

The following instruments will be used and are submitted for review:

(1) Demographic information sheet. This sheet assesses general information such as age, years of education, etc.

(2) Structured Clinical Interview for DSM-IV (SCID; First, Spitzer, Gibbon et al., 1995). This instrument will be used to determine the Axis I psychiatric diagnosis(es).

(3) Structured Clinical Interview for DSM-IV Axis II Personality Disorders (SCID-II; First et al., 1997). Patients will complete the SCID-II self-report questionnaire; for any personality disorder for which the patient's report approaches criterion (number of criteria required minus 1), the rater will administer all interview questions for that personality disorder.

(4) Yale Brown Obsessive Compulsive Scale modified for BDD (BDD-YBOCS). This reliable and valid 12-item semi-structured clinician-administered scale, which was adapted from the Y-BOCS (Goodman et al., 1989), rates current severity of BDD symptoms (Phillips et al., 1997). It will be the study's primary outcome measure. The BDD-YBOCS has excellent interrater and test-retest reliability (ICC for total score=.99 and .88, respectively), internal consistency (Cronbach's alpha=.80), convergent validity ($r=.55$ with the CGI), and sensitivity to change with treatment (Phillips et al., 1997).

(5) BDD-Symptom Scale (BDD-SS) The PI developed the BDD-SS to rate the severity of specific BDD symptoms.

(6) Clinical Global Impression Scale (CGI) This global rating scale, which ranges from 1 (very much improved) to 7 (very much worse) on levels of improvement (CGI-I) and from 1 (normal, not at all ill) to 7 (extremely ill) on severity (CGI-S), is commonly used in pharmacotherapy trials (Guy, 1976). The CGI will be a secondary outcome measure and will also be used to determine clinical deterioration of BDD.

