Data Collection and Storage

Self-report measures will be collected using RedCap™, a platform for electronic data capture that streamlines data collection and management, and ensures data integrity, resulting in improved data quality. RedCap allows researchers to design and implement study surveys for collecting, storing, retrieving, and manipulating data electronically. Participants and/or research staff enter survey responses into electronic assessment forms. This electronic data capture obviates the need for subsequent data entry by staff, thus minimizing human error.

These surveys are completed securely via the internet by using any device with standard web access and browsers. For this study, participants and staff will complete the electronic assessments on computer terminals at the research site under the supervision of study staff. All users will have defined roles and privileges pre-determined by the system administrator. Thus, the PI can determine the level of access for each study staff such that only a limited number of people have access to sensitive study data.

Medical Assessment

At the initial study visit, one of the study physicians will evaluate the participant with regard to the medical and psychiatric exclusion criteria to be sure that none are met. Participants will be monitored in an ongoing manner for side effects or any adverse reactions to the study medication, and further evaluations will occur at any other times as necessary. Participants may contact the study physicians at any time to discuss their medication, side effects, or adverse reactions.

Also at this time a urine pregnancy test will be performed for women of child-bearing potential. If the test is positive, the participant will be

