Evaluation of Population Structure. It has been well recognized that ethnic admixture or population stratification may confound case-control genetic association studies, although the importance of this phenomenon has been debated (Freedman et al., 2004; Wacholder et al., 2002). Nevertheless, we will evaluate the possibility of confounding due to population stratification, by typing a panel of 100 informative unlinked (null) SNPs. The main approach used will be that described by Purcell and Sham (2004), which implements a method very similar to that of Pritchard et al. (2001) and Satten et al. (2001). All these approaches look for Hardy-Weinberg disequilibrium and LD between unlinked markers, and probabilistically break down the sample to a number of subgroups, within which Hardy-Weinberg equilibrium and linkage equilibrium hold (as one would expect in a homogeneous population). We will evaluate population structure by performing analyses using the L-POP program (Purcell et al., 2004). Because the sample is expected to be primarily Caucasian, if more than one subgroup is detected, we expect that only one subgroup will have sufficient power for analysis. Thus our analyses would focus on the largest subgroup.

7. Risks and Discomforts

Patients may feel uncomfortable due to the sensitive nature of the questions they may be asked.

Side effects. The potential side effects associated with the administration of DCS include drowsiness, headache, prolonged or momentary dizziness, seizures, confusion, hallucinations, weakness, coma, rash, vitamin B₁₂ deficiency and/or folate deficiency (both of which may cause weakness and anemia (low blood counts)), liver enzymes increases (which could cause weakness or bleeding), and shaking. However, these side effects are most commonly related with doses greater than 500mg/day, which is five times what is administered in this study. The use of DCS at doses of 100 mg (as in this study) does not appear to be associated with significant emergent adverse effects. Indeed, in our recent trial examining the efficacy of DCS augmentation of behavior therapy for individuals with OCD no subjects reported any side effects as a result of the study medication.

Interactions.

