(1) Intake of alcohol at the same day may increase the possibility and risk of epileptic episodes. Thus, we will exclude patients with current alcohol dependence. Furthermore, we will instruct the patients not to consume any alcohol 12 hours prior to and 24 hours after receiving the study medication. To ensure that patients have not consumed alcohol prior to taking the study medication we will administer a saliva test to measure BAC levels immediately before dispensing the medication.

(2) Intake of Isoniazid at the same day may result in increased CNS side effects. Thus, we will exclude patients who currently take Isoniazid.

Optional Genetics Component

There is a risk associated with the sensitivity of the genetic information. The results of genetic analyses will be kept confidential and will not be returned to participants in this study. Consequently, the potential risks of subjects learning sensitive genetic information or of discrimination related to participation in a genetic study should be avoided. There is a theoretical risk of discrimination by employers or insurers should subjects' enrollment into or the results of the study unintentionally become known despite procedures in place to maintain confidentiality. The following steps will be taken to protect the confidentiality and privacy of the genetic data:

- a. No genetic research data will be entered into the medical record.
- b. The results of the genetic analyses will not be shared with participants or their family members.
- c. Only coded identifiers, rather than personal identifiers, will be used in any analytic datasets. The genetic laboratory will not have access to personal identifiers.

To protect confidentiality, information about subjects will be stored in research files identified only by code. The code key connecting IDs to identifying information will be kept in a separate secure location at the research site at which a participant is enrolled. Data in databases is similarly identified only by coded ID number and is password-protected.

Minimizing of Risks and Safety Reporting. Subjects will be monitored in an ongoing manner for side effects or any adverse reactions to the study medication. The study physicians, Drs. [name] and [name], will review all reports of adverse events and forward them to the IRB. Patients may also contact them at any time to discuss their medication, side effects, or adverse reactions.

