Adverse event reporting: In case of an adverse event and in accordance with Partners Human Research Committee Adverse Event Reporting Guidelines, we will complete the appropriate adverse event form and forward it to the IRB within the required time frame for reporting.

8. Potential Benefits

Patients may benefit by experiencing some relief from their BDD symptoms. Our research will help us better understand what treatments are beneficial in this disorder.

9. Monitoring and Quality Assurance

[name] and [name] will be responsible for ensuring that all study procedures are conducted according to the IRB-approved protocol and reviewing the accuracy and completeness of source documents. [name] and [name] will meet with [name] regularly to discuss the study procedures and progress. Drs. [name] and [name] will be responsible for ensuring that the study treatment is delivered appropriately.

Subjects will be monitored in an ongoing manner for side effects or any adverse reactions to the study medication. The study physicians will review all reports of adverse events and forward them to the IRB according to Partners guidelines. Participants may also contact the study physicians at any time to discuss their medication, side effects, or adverse reactions. The PI, in collaboration with the study physicians will ultimately be responsible for determining whether the research should be altered or stopped.

Participants will be withdrawn from the study if their clinical condition deteriorates substantially. Deterioration will be defined by a rating of 6 (much worse) or 7 (very much worse) on the CGI-I. Participants may also be withdrawn if in the judgment of the PI or therapist remaining in the study poses a substantial risk to the participant or a higher level of care is needed.

In case of an adverse event and in accordance with Partners Human Research Committee Adverse Event Reporting Guidelines, we will complete the appropriate adverse event form and forward it to the IRB within the required time frame for reporting.

10. References

Alliez, J., & Robin, M. (1969). Aspects psycho-pathologiques de la defiguration leur relation avec dysmorphophobie [Psychopathologic aspects of disfiguration; their relation to dysmorphophobia]. *Ann Med Psychol*, 2, 479-94.

- American Psychiatric Association (1994). Diagnostic and statistical manual of mental disorders, 4th edition. Washington, DC, American Psychiatric Association Press.

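### The plan specifies no prompted side-effect question and no adverse-event summary by arm, so a low side-effect count could not be told from not having asked

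*Combined protocol and SAP*

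**What the plan says.** **Collection.** Section 7 (Minimizing of Risks and Safety Reporting) states: "Subjects will be monitored in an ongoing manner for side effects or any adverse reactions to the study medication". It then adds a second route: "Patients may also contact them at any time to discuss their medication, side effects, or adverse reactions". The Medical Assessment part of Section 5 repeats the monitoring commitment and adds that "further evaluations will occur at any other times as necessary". Sections 7 and 9 say that, when an adverse event has occurred, "we will complete the appropriate adverse event form and forward it to the IRB within the required time frame for reporting". The study physicians review all reports.

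**Instruments.** The Psychological Assessments part of Section 5 opens its list with "The following instruments will be used and are submitted for review" and names 25 instruments (the twentieth is misnumbered). None is described as a measure of side effects. The per-session assessments are BDD symptoms, CGI-I and depressive symptoms. Beyond these, "comprehensive assessments of BDD symptoms, mood state and cognitions to assess the outcome of therapy will be given at midtreatment", and again at post-treatment and at 1 and 6 months. A detailed assessment schedule is said to be submitted separately; it is not in the documents.

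**Analysis.** Section 6 compares the arms on the BDD-YBOCS and on secondary measures of symptoms and functioning. It contains no safety variable and no tabulation of adverse events. The optional unblinding after every ten subjects is for efficacy.

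**Expected effects.** Section 7 lists specific possible effects of DCS, among them drowsiness, headache, dizziness, confusion, hallucinations, seizures, weakness and shaking. As reassurance it cites the earlier OCD trial, in which "no subjects reported any side effects as a result of the study medication".

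**The concern.** The plan knows which symptoms to look for but schedules no question about them. A symptom that nobody asks about at the time cannot be recovered at analysis.

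Section 2 presents the trial as a source of pilot data for a larger study, so what it reports on tolerability is likely to be carried forward. If few or no side effects are recorded, a reader could not tell whether few occurred or few were sought. The statement quoted from the OCD trial has the same limit: the documents do not say how side effects were elicited there. Section 9 also makes the PI, with the study physicians, responsible for deciding whether the research is altered or stopped, and no systematic safety summary by arm is planned to inform that decision.

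**Working it through.** The plan gives no figure on this point. Its one design calculation (80% power for d = 0.78) concerns the BDD-YBOCS, and nothing below depends on it.

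**1. What would bring a symptom into the record?**

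| Route | What starts it | Fixed question and time? | Used in Section 6? |
|---|---|---|---|
| Ongoing monitoring (Sections 5, 7, 9) | not stated | no | no |
| Further evaluations (Section 5) | judged necessary | no | no |
| Contact with physicians (Sections 5, 7, 9) | the patient | no | no |
| Adverse event form (Sections 7, 9) | a known event | records, does not elicit | no |
| Per-session measures (Section 5) | every session | yes, for BDD symptoms, CGI-I and depression | efficacy only |

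No route combines a fixed side-effect question, a fixed time and a planned summary.

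**2. Timing.** Section 1 says of DCS: "Its half-life in serum is approximately 7 to 15 hours". Dosing is one hour before the session. Assuming a session of 1 to 2 hours (length not stated) and ignoring absorption, the share of drug left at the end is:

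- 1-hour session, 2 h after dosing: 2^(-2/7) = 82% to 2^(-2/15) = 91%.
- 2-hour session, 3 h after dosing: 2^(-3/7) = 74% to 2^(-3/15) = 87%.

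Sessions are weekly, so 168 h pass before the next one: 168/15 = 11 to 168/7 = 24 half-lives. Much of the exposure therefore falls away from the clinic, and effects there reach the record by recall or by the patient making contact. These figures describe drug remaining, not events missed.

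**3. What zero events would mean.** With n = 25 on DCS (Section 2), the exact one-sided 95% upper bound for the proportion of patients affected is 1 − 0.05^(1/25) = 11.3%. The two-sided 95% interval has upper limit 1 − 0.025^(1/25) = 13.7%. Both assume that every patient was asked and answered.

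**4. Illustration of incomplete capture.** Let p be the true proportion affected and f the share of affected patients who reach the record. The documents give neither, so both are assumptions. The chance of recording no events in 25 is (1 − p·f)^25:

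| True p | f = 100% | f = 50% | f = 25% | f = 10% |
|---|---|---|---|---|
| 10% | 7.2% | 27.7% | 53.1% | 77.8% |
| 20% | 0.4% | 7.2% | 27.7% | 60.3% |

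**5. What full questioning could deliver at 25 per arm.** An effect with a true rate of 10% would appear at least once with probability 1 − 0.90^25 = 92.8%; at 5%, 1 − 0.95^25 = 72.3%. A formal comparison would be weak. Fisher's exact test gives p = 0.0502 for 5 v 0 and p = 0.022 for 6 v 0, and its power for true rates of 30% v 10% is 30%. The comparison by arm should therefore be descriptive.

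**The case against.** The strongest reply is that the plan does commit staff to monitor. Patient contact is an additional route, participants are seen weekly, and each dose is taken in the therapist's presence. The 25 instruments stand under a psychological heading, while side effects fall under Medical Assessment, so their absence from that list is weak evidence alone. Item wordings are not reproduced, and the separate schedule might contain a side-effect item.

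This stands to a point. A reader might infer that nobody will ask, or that capture is purely passive. The documents do not say so; they leave the matter open. But no passage fixes a question or a time, and Section 6 plans no summary wherever the data come from.

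Three other stronger readings also fail:

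- **Exposure cannot be separated from drug.** Both arms receive the same exposure sessions under blinded randomisation, so the placebo arm supplies that contrast for any event recorded. The drug-free sessions 1–2 do not, because they are mainly cognitive and exposure starts with dosing. They can show pre-existing symptoms only.
- **The session 10 dose has no follow-up.** It has no later therapy session, and it accounts for 25 of 25 × 8 = 200 active doses (12.5%). But post-treatment, 1-month and 6-month assessments follow. What they lack, as described, is a side-effect question.
- **The true upper bound is 23% or 45%.** Those values are 11.3% divided by assumed capture of 50% or 25%. They illustrate sensitivity and are not results.

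**Conclusion.** The concern holds as a gap in specification with a real consequence. The documents provide no defined elicitation of side effects and no planned adverse-event summary by arm. Followed as written, the trial may under-record the symptoms in its own list, and a low count would be uninformative. The 11.3% bound from zero events in 25 requires that all 25 were asked, which the plan does not secure. How much would be missed cannot be computed from the documents; the table of capture shares shows only how strongly the answer depends on it.

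The conclusion assumes that the unseen assessment schedule contains no side-effect item. If it does, the collection part falls away and the missing summary in Section 6 remains. Nothing here implies that DCS at the study dose is unsafe, or that the primary efficacy analysis is affected. Prompted collection would not remove the limit set by 25 per arm; it would make the 11.3% bound valid.

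**What to change.** **Sections 5 and 7.** Add a short checklist of the Section 7 symptoms that a patient can report, plus an open item for anything else, with severity and onset relative to dose. Complete it by self-report in RedCap with the existing per-session questionnaires:

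- at sessions 1–2, to record pre-existing symptoms only;
- at sessions 3–10, before dosing, for the interval since the last visit;
- at the post-treatment and 1-month visits, so that the session 10 dose is covered.

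Reports go to the study physicians through the existing review route. If the separate assessment schedule already has such an item, cite it here.

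**Section 6.** Add one descriptive table by arm of symptoms that are new or worse since sessions 1–2, with exact confidence intervals. No formal test is needed.

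**Cost.** One form, a few minutes per visit, and one table, with no extra visits and no change in sample size. Prompting will raise the count of minor events in both arms, which is why the placebo column is needed. Symptom answers could also hint at allocation. That risk is small and is limited by using self-report and keeping the answers from the efficacy rater.
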